#### **(2) Renal Replacement Therapy**

**Definition:** Use of artificial methods such as hemodialysis to replace renal function for removal of metabolic waste and regulation of fluid and electrolyte balance in the event of severe renal failure.

**Assessment Method:** Indications include volume overload unresponsive to diuretics; severe hyperkalemia ( $>6.5$  mmol/L) or rapidly rising potassium with cardiotoxicity; severe metabolic acidosis ( $pH <7.1$ ); acute kidney injury (AKI) patients unable to tolerate fluid balance and metabolic fluctuations; refractory fluid overload, septic shock, severe electrolyte or acid-base imbalance, acute hepatic failure, severe tumor lysis syndrome, heat stroke, etc. AKI diagnosis and grading are

based on the KDIGO (Kidney Disease: Improving Global Outcomes) criteria (Table 3).

**Table 3 Definition and Grading Criteria of Acute Kidney Injury**

Acute Kidney Injury	
Definition	Meets any one of the following: a. Increase in serum creatinine $\geq 0.3\text{mg/dL}$ ( $26.5\mu\text{mol/L}$ ) within 48 hours; b. Increase in serum creatinine to $\geq 1.5$ times baseline, known or presumed to have occurred within the prior 7 days; c. Urine output $<0.5\text{ mL/kg/h}$ for 6 hours.
Grading Criteria	Stage 1: Serum creatinine rises by an absolute value of $\geq 0.3\text{ mg/dL}$ ( $26.5\mu\text{mol/L}$ ), or increases by $\geq 0.5$ times but less than 1 time relative to baseline; or urine output $<0.5\text{ mL/kg/h}$ for $\geq 6$ hours but $<12$ hours.
	Stage 2: Serum creatinine increases by $\geq 1$ time but less than 2 times relative to baseline; or urine output $<0.5\text{ mL/kg/h}$ for $\geq 12$ hours but $<24$ hours.
	Stage 3: Any of the following: a. Serum creatinine $\geq 4.0\text{ mg/dL}$ ( $353.6\mu\text{mol/L}$ ); b. Serum creatinine increases by $\geq 2$ times relative to baseline; c. Urine output $<0.3\text{ mL/kg/h}$ for $\geq 24$ hours; d. Anuria for $\geq 12$ hours; e. Initiation of renal replacement therapy.

\* Due to intraoperative management interventions (such as mannitol administration), hourly urine output on the day of ICU admission will not be included in the assessment criteria for acute kidney injury.

**Observation Time Points:** Postoperative 1 to 3 days, and discharge day / postoperative 30 days.

### **(3) Stroke**

**Definition:** Acute onset of new focal or global neurological deficit.

**Assessment Method:** At least one of the following: altered level of consciousness, hemiplegia, hemiparesis, numbness or sensory loss affecting one side of the body, aphasia or language disturbance, hemianopia, amaurosis, or other focal/global neurological deficits lasting  $\geq 24$  hours; or neurological deficit resulting in death. All events must be confirmed by imaging and corresponding reports.

**Observation Time Points:** Postoperative 1 to 3 days, and discharge day / postoperative 30 days.

### **(4) Paraplegia**

**Definition:** New-onset ischemic spinal cord injury postoperatively, resulting in motor and sensory dysfunction of both lower limbs below the level of injury, with corresponding neurological signs.

**Assessment Method:** Graded according to the American Spinal Injury Association (ASIA) Impairment Scale with stroke excluded (**Table 4**).

**Table 4. American Spinal Injury Association (ASIA) Impairment Scale**

Grade	Clinical Manifestations
A (Complete injury)	No sensory or motor function preserved.
B (Incomplete injury)	Sensory function is preserved below the neurological level, including the sacral segments, but no motor function is preserved.
C (Incomplete injury)	Motor function is preserved below the neurological level, but more than half of key muscles have a muscle grade less than 3.
D (Incomplete injury)	Motor function is preserved below the neurological level, and at least half of key muscles have a muscle grade of 3 or greater.
E (Normal)	Sensory and motor functions are normal.

Note: Muscle strength grading: 0-No movement in the lower limbs; 1-Lower limb movement cannot overcome gravity; 2-Limb movement can overcome gravity; 3-Able to stand with assistance; 4-Able to walk with assistance; 5-Normal.

**Observation Time Points:** Postoperative 1 to 3 days, and discharge day / postoperative 30 days.

## Secondary Outcome Measures

### (1) Circulatory Arrest Time

**Definition:** time interval between ceasing and restarting cardiopulmonary bypass when core temperature reaches moderate hypothermia.

**Assessment Method:** According to the cardiopulmonary bypass record sheet.

**Observation Time Point:** Operation day.

### (2) Cardiopulmonary Bypass Time

**Definition:** start-to-end time of cardiopulmonary bypass to complete aortic repair.

**Assessment Method:** According to the cardiopulmonary bypass record sheet.

**Observation Time Point:** Operation day.

**(3) Duration of Mechanical Ventilation**

**Definition:** time interval between mechanical ventilation and extubation after operation.

**Assessment Method:** According to the intensive care unit record sheet.

**Observation Time Point:** Discharge day / postoperative 30 days.

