## **Rationale for Study Design**

- (1) Prospective: Prospective design minimizes bias. Standardized enrollment criteria, methods, process, and outcome measures, clarify the causal relationship.
- (2) Multicenter: Multicenter trials can enroll participants rapidly, resulting in shorter clinical trial periods, good extrapolation, and minimal bias caused by systematic errors.
- (3) Three-arm: This study involves two technical optimizations: temperature change from moderate temperature to mild temperature; unilateral antegrade cerebral perfusion changed to bACP. Due to the inability to control two variables simultaneously using a two-arm design, we plan to establish three groups for a randomized controlled trial.
- (4) Randomized: This trial uses randomization at each center. Each participant successfully screened has equal opportunity and is randomly assigned to Group 1 (arch-clamping technique under mild hypothermia), Group 2 (arch-clamping technique under moderate hypothermia) and Group 3 (Sun's procedure using bilateral antegrade cerebral perfusion) in a 1:1:1 ratio without the investigator nor the participant's personal preferences influence.
- (5) Open-label: The three surgical procedures differ significantly in terms of manipulation, so it is impossible to blind the researchers and participants.
- (6) Parallel-controlled: Sun's procedure as a TAR+FET technique, is the standard surgical treatment for ATAAD.

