**(4) Length of ICU stay**

**Definition:** time interval from ICU admission to transfer or death.

**Assessment Method:** According to the intensive care unit record sheet.

**Observation Time Point:** Discharge day / postoperative 30 days.

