#### **Visit 5: Day of Discharge/Postoperative Day 30 ( $\pm 7$ days)**

(1) Collect symptoms and physical examination findings.

(2) Collect laboratory tests, including complete blood count, biomarkers of liver and renal function, etc.

(3) Collect the occurrence of death, RRT, stroke, and paraplegia.

(4) Collect ICU parameters:

- Duration of mechanical ventilation: Time interval between mechanical ventilation and extubation after operation.
- Length ICU of stay: Time interval from ICU admission to transfer or death.
- Collect imaging data, including CTA and echocardiography.

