## **Secondary Endpoint Analysis**

Analysis of secondary endpoints will be conducted based on both FAS and PPS.

Statistical analysis methods will follow the general principles described above.

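### Ventilation time and ICU stay are single intervals with no rule for reintubation or ICU readmission, so repeat time is left out on the plain wording and may be recorded differently by centre

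*Combined protocol and SAP*

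**What the plan says.** Under Secondary Outcome Measures, item (3) defines ventilation time as the "time interval between mechanical ventilation and extubation after operation". Its source is given as "According to the intensive care unit record sheet" and its observation point as "Discharge day / postoperative 30 days". Item (4) defines ICU stay as the "time interval from ICU admission to transfer or death", with the same source and observation point.

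Visits 3, 4 and 5 repeat both definitions; Visit 5, for example, has "Duration of mechanical ventilation: Time interval between mechanical ventilation and extubation after operation". The Study Flowchart marks both items at these three visits, with no instruction on how the entries are combined.

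Rationale for Study Design, item (5), states that "it is impossible to blind the researchers and participants". Measures to Control Bias lists prospective design, multicentre design, training and uniform eligibility screening. It describes no blinded assessment and no criteria for extubation or ICU transfer.

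On analysis, Secondary Endpoint Analysis says only "Statistical analysis methods will follow the general principles described above". For quantitative data those principles allow analysis of variance or a rank-sum test, on both the full analysis set and the per protocol set.

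**The concern.** A single interval that stops at extubation, or at transfer out of ICU, has no place for a second episode. Take a patient extubated at 12 h and later put back on the ventilator for four days. Read plainly, the definition records 12 h. Another centre could reasonably enter the time to final extubation, or the total ventilated time. The same choice arises for a patient who leaves the ICU and returns.

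Both stop points are clinical decisions, unlike bypass time, and no blinded team is described. If one arm is extubated or transferred earlier and more of its patients come back, the outcome as defined can credit the early decision without charging the return.

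The protocol's study summary names ventilation time and length of stay among the measures by which validity and safety are judged. The other two secondary outcomes are intraoperative times, so these are the only secondary outcomes that describe recovery.

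**Working it through.** The plan states no figure for this point, so there is nothing to reproduce. The check has a textual part and an illustration on assumed values.

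**Text.** Four places were compared: the two definitions, their repetition at Visits 3–5, the flowchart, and the rules for missing and abnormal values. None mentions a repeat episode, and none contains a word that selects the first, the last or the sum of episodes. The observation window runs to discharge or day 30, so a repeat episode could be seen. The definition does not say to add it.

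**Uncounted time (assumed inputs).** The documents give neither a reintubation rate nor a length of repeat ventilation. Let r be the share reintubated and L the extra hours. The mean time left out per patient is r × L.
- r = 5%, L = 48 h: 0.05 × 48 = 2.4 h
- r = 15%, L = 96 h: 0.15 × 96 = 14.4 h

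For scale, Table 1 of the Background reports a mean intubation time of 13.6 h with arch-clamping (n = 39) and 34.1 h with the conventional procedure (n = 40), a difference of 13.6 − 34.1 = −20.5 h.

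**Effect on a difference in means.** The error in the difference is r₁L₁ − r₂L₂.
- Equal arms (5% and 5%, same L): error 0. On Table 1 the difference stays at −20.5 h.
- 15% versus 5%, L = 48 h: 0.10 × 48 = 4.8 h. On Table 1, −20.5 + 4.8 = −15.7 h.
- 15% versus 5%, L = 96 h: 0.10 × 96 = 9.6 h. On Table 1, −20.5 + 9.6 = −10.9 h.

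The Table 1 lines treat its means as times to first extubation, which is itself an assumption.

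**Effect on a rank-sum test.** Take the same 15% versus 5%, identical first episodes in both arms, and every repeat case moved to the top ranks with ties split evenly. The probability that a patient in the first arm has the longer time is

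0.15 × 0.95 + 0.5 × (0.85 × 0.95 + 0.15 × 0.05) = 0.1425 + 0.4075 = 0.55,

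against 0.50 if repeat time is ignored. With 102 per arm, the null standard error is √[(102 + 102 + 1) / (12 × 102 × 102)] = √(205 / 124,848) ≈ 0.0405. The shift is 0.05 / 0.0405 ≈ 1.2 standard errors.

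**What Table 1 can tell us.** In a sample of n, no value can lie further from the mean than SD × (n − 1)/√n. For the arch-clamping arm (SD 2.2 h) this is 2.2 × 38/√39 ≈ 13.4 h, so no recorded time exceeded about 27 h. Either no long repeat episode occurred in those 39 patients or none was counted. The table cannot separate the two, so it gives no reintubation rate.

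**The case against.** The strongest reply is that silence is not a rule. The protocol never says first extubation or first transfer. It collects both items at three visits and observes to discharge or day 30, so a centre could enter total time. That stands. A reader might infer that a reintubated patient will always score as a fast recovery, but the documents do not establish this. What they support is that the plain single-interval wording leaves repeat time out and that practice may vary between centres. The reply therefore narrows the point and leaves the need for a rule in place.

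Second, the hours rest wholly on assumed rates, and nothing in the documents suggests that reintubation differs between arms. That also stands. With equal repeat episodes the difference in means is unbiased, and under the rank-sum option even a threefold difference in frequency shifts the result by only about 1.2 standard errors. The plan does not fix which test applies.

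Third, a reader might infer that the definitions hide neurological complications. They do not: stroke and paraplegia are components of the primary composite and are collected at every postoperative visit. Some failed extubations would also be reported as serious adverse events through prolonged hospitalization, although that does not correct the two durations.

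Fourth, that the clinicians deciding on extubation and transfer know the arm is an inference. The protocol refers to researchers and participants and does not name ICU staff. The inference is reasonable, since no blinded team is described, but it does not show that decisions would in fact be tilted.

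**Conclusion.** The point holds as a minor one. Two of the four secondary outcomes have no rule for repeat episodes. As written they leave out time after reintubation or ICU readmission, and they are open to inconsistent recording across seven centres. In an open-label trial this can bias the comparison, but only if repeat episodes differ between arms in frequency or length.

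The size is unknown. On the assumption of 5–15% reintubated for 48–96 h, 2.4–14.4 h per patient on average is uncounted. A contrast of 15% versus 5% would shift the difference in means by 4.8–9.6 h, equal arms would shift it by nothing, and the effect on a rank-sum test would be small. No corresponding figures were worked for ICU stay, for which the documents give no readmission rate.

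Both outcomes lie outside the fixed-sequence test, so the primary conclusion and the 306-patient sample size are unaffected.

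**What to change.** Rewrite the two definitions, and their copies at Visits 3–5, as follows:

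- **Ventilation time:** total hours of invasive ventilation from end of surgery to day 30, summed over all episodes including reintubation.
- **ICU stay:** total ICU hours over the same window, summed over all episodes including readmission.
- **Still ventilated or in ICU at day 30:** count to day 30.
- **Deaths:** state a rule so that death does not score as a short duration, for example days alive and free of ventilation or ICU, or ranking deaths as worst. Summing episodes alone does not solve this. ICU stay now ends at death, and the ventilation definition is silent on death before extubation.
- **Reporting:** give the numbers reintubated and readmitted to ICU by arm.

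The ICU record sheet is already the source, so the cost is two definitions, a repeatable row on the eCRF and slightly more abstraction for the few patients with a second episode.

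The change concerns measurement only and alters no clinical rule. It does not remove unblinded discretion over when to extubate or transfer. It only stops that discretion from being rewarded when the patient returns to the ventilator or the ICU.

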**(4) Length of ICU stay**

**Definition:** time interval from ICU admission to transfer or death.

**Assessment Method:** According to the intensive care unit record sheet.

**Observation Time Point:** Discharge day / postoperative 30 days.

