**Table 1. The early-outcomes between arch-clamping technique and conventional TAR + FET procedure**

[figure not shown]
Variables	Arch-clamping	Conventional TAR	P value
	Technique (n = 39)	+ FET Procedure (n = 40)	
Circulatory arrest time, (min)	4.1 ± 0.6	23 ± 8.8	0.001
Cross Clamp time, (min)	96.9 ± 4.4	127.1 ± 13.3	0.001
CPB time, (min)	158.4 ± 6.8	198.0 ± 12.6	0.001
Postoperative drainage, (ml) *	465 ± 95.5	440.0 ± 100.5	0.260
Intubation time, (h)	13.6 ± 2.2	34.1 ± 14.3	0.001
Red blood cells transfusion, (U)	4.5 ± 1.5	4.1 ± 1.3	0.210
CRRT, n (%)	1 (2.6)	8 (20)	0.029
Stroke, n (%)	1 (2.6)	2 (5)	0.571
Thirty-day death, n (%)	2 (5)	3 (7.5)	1.000

Values are presented as n (%) or mean ± standard deviation. \* Postoperative 12-hour Drainage; *CPB*, Cardiopulmonary bypass; *CRRT*, Continuous renal replacement therapy.

Our team also try to elevate the core temperature of the circulatory arrest over 28°C. We compared the early outcomes of arch-clamping technique under different temperatures. The results demonstrated that the CPB duration and cross-clamp time were significantly reduced in the mild hypothermia group compared to moderate hypothermia group. Meanwhile, the mild hypothermia group has lower mortality and morbidities, especially for the incidences of stroke, spinal cord injury, and continuous renal replacement therapy (Figure 2) [11]. Our previous studies also found that using bACP as a brain protective strategy can significantly reduce the incidence of permanent neurological dysfunction [12,13]. Therefore, we hypothesize that arch-clamping technique combined mild hypothermia and bACP as a surgical bundle can be effective in minimizing the circulatory arrest time and mitigating multi-organ injury due to temperature changes and prolonged CPB duration.

In summary, we designed a multicenter randomized controlled trial to observe the 30-day and 1-year outcomes of patients with ATAAD after operation, seeking to validate the efficacy and safety of arch-clamping technique under mild hyperthermia

using bACP for the treatment of ATAAD.

**Figure 2.** Postoperative outcomes of using the arch-clamp technique in treating with ATAAD at different temperatures. Cardiopulmonary bypass time and cross-clamp time were presented as minutes; Total hospital stay was presented as days; Other variables were presented as n (%). *CRRT*, Continuous renal replacement therapy.

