## **Analysis Populations**

Statistical analyses will be based on clearly defined analysis populations prior to data analysis in this study:

**Full Analysis Set (FAS):** The set constructed according to the intention-to-treat principle, including all subjects who participated in the study and received TAR+FET treatment.

**Per Protocol Set (PPS):** A subset of FAS, including all subjects who completed the trial without major protocol violations.

Baseline data will be analyzed based on the FAS, and analyses of primary and secondary outcomes will be performed on both FAS and PPS.

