## **Statistical Methods**

### **General Principles**

(1) Descriptive statistics: For quantitative variables, the number of cases, mean, standard deviation, median, interquartile range, minimum, and maximum values will be reported. For qualitative variables, absolute and relative frequencies will be reported.

(2) Inferential statistics: Unless otherwise specified, two-sided tests will be used, and a two-sided P-value less than or equal to 0.05 will be considered statistically significant. Comparisons of quantitative data between groups will be performed by analysis of variance or rank-sum test; comparisons of qualitative data will use the chi-square test or Fisher's exact test; multicategorical or ordinal data will be analyzed using the Cochran-Mantel-Haenszel (CMH) test.

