## **Handling of Missing and Abnormal Values**

(1) Handling of missing data: No imputation of missing data will be conducted; analysis will be based on the data actually obtained.

(2) Handling of erroneous data: Investigators shall make written corrections to erroneous data. The database can only be locked after all errors have been corrected.

(3) Handling of unreasonable data: Investigators shall make written adjustments to unreasonable data. The database can only be locked after all unreasonable data entries have been addressed.

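### ICU stay ends at death and ventilation time has no rule for death, so two of the four secondary outcomes can be distorted, in a direction that depends on when patients die (minor).

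*Combined protocol and SAP*

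**What the plan says.** Under Secondary Outcome Measures, length of ICU stay is the "time interval from ICU admission to transfer or death". Duration of mechanical ventilation is the "time interval between mechanical ventilation and extubation after operation". Both definitions recur at Visits 3, 4 and 5, and both outcomes are read at discharge or postoperative day 30.

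The Secondary Endpoint Analysis section adds no method of its own: "Statistical analysis methods will follow the general principles described above". Those principles state: "Comparisons of quantitative data between groups will be performed by analysis of variance or rank-sum test". Handling of Missing and Abnormal Values states: "No imputation of missing data will be conducted; analysis will be based on the data actually obtained".

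Death is a component of the primary composite, but nothing links it to these two durations. The plan contains no worst-rank score, ICU-free or ventilator-free days, competing-risk method or survivor-only rule.

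**The concern.** The two definitions treat death differently, and neither treats it as a bad outcome.

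- **ICU stay.** Death closes the interval in the same way as transfer out. A patient who dies on day 1 gets a value of one day, which a rank-sum test or a mean reads as better than almost any survivor's stay. This follows from the definition as written.
- **Ventilation.** The definition names only extubation as the end. A patient who dies intubated has no defined value, and with no imputation would probably be left out. This is an inference from silence combined with the missing-data rule. The section does not say that such patients are excluded.

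These are half of the secondary outcomes, and the protocol summary lists ventilation time and length of stay among the measures of validity and safety. If mortality differs between arms, a difference in either duration could partly reflect how deaths were scored rather than how fast survivors recovered.

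**Working it through.** **Arm size.** The documents give no power or distribution for either duration, so the only stated figure to reproduce is the arm size. For 13% vs 30%, one-sided 0.025, 80% power, pooled variance, mean rate 0.215:

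n = [1.96·√(2·0.215·0.785) + 0.8416·√(0.13·0.87 + 0.30·0.70)]² / 0.17² = (1.139 + 0.478)² / 0.0289 = 90.5, so 91 per group. With 10% dropout, 91/0.9 = 101.1, so 102 per group and 306 in total. Both match the plan.

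**Inputs for ICU stay.**
- From the documents: the definition; the rank-sum test; the rule that "two-sided tests will be used, and a two-sided P-value less than or equal to 0.05 will be considered statistically significant"; and the Table 1 row "Thirty-day death, n", with 2/39 (5%) vs 3/40 (7.5%).
- Assumed: survivors' stay is the same in both arms, lognormal with median 4 days and log-SD 0.6; 91 per arm; mortality 5% vs 15%; all deaths occur in ICU. Time of death is varied, with log-SD 0.8 except where all deaths are on day 1.

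**Formula.** With equal survivor stays, the shift in mean equals the mortality difference times (survivors' mean stay − mean time to death).
- Survivors' mean = 4·exp(0.6²/2) = 4·1.197 = 4.79 days.
- Mean time to death = median·exp(0.8²/2) = median·1.377.

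The last column is from simulation; chance alone gives about 2.5%.

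| Time of death | Mean time to death (days) | 0.10 × (4.79 − mean): deadlier arm looks | Trials significantly favouring deadlier arm |
|---|---|---|---|
| all on day 1 | 1.00 | 0.38 day shorter | about 22% |
| median 1.5 days | 2.07 | 0.27 day shorter | about 12% |
| median 3 days | 4.13 | 0.07 day shorter | about 4 to 5% |
| median 5 days | 6.89 | 0.21 day longer | about 1% |
| median 10 days | 13.77 | 0.90 day longer | below 1% |

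The sign changes where the mean time to death equals 4.79 days, a median of 4.79/1.377 = 3.5 days under these assumptions.

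**At Table 1 mortality.** The gap is 2.5 points. Even with every death on day 1 the shift is 0.025·(4.79 − 1.00) = 0.09 day, and the total two-sided rejection rate is about 5.4% against a nominal 5%.

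**Ventilation.** Assume a median of 20 h, log-SD 0.8, 102 per arm, more deaths among the long-ventilated, and no value for patients who die. The deadlier arm's mean is shorter by 0.7 h (7.5% vs 5%), 2.5 h (15% vs 5%) and 4.0 h (20% vs 5%). For scale, the Table 1 intubation times differ by 34.1 − 13.6 = 20.5 h.

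**The case against.** The strongest case against is that direction and size rest on assumptions that the documents do not supply. They give no ICU-stay distribution and no times of death. The 22% figure needs every death on day 1 and a 10-point mortality gap that appears nowhere in the plan. At the only mortality figures given, the shift is near nil, and if deaths come late the ICU rule counts against the deadlier arm. All of this stands, and it is why the result is given as a range.

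A reader might infer that a true advantage of Group 1 would be hidden or reversed. The documents do not support that. For ventilation, an assumed bias of 0.7 to 4.0 h cannot hide a difference like the 20.5 h in Table 1. For ICU stay, some loss of power can be constructed. If Group 1 survivors truly stay 20% less and all deaths are on day 1, the chance of detecting this falls from about 60% at equal 5% mortality to about 46% at 5% vs 7.5%. Both the effect and the death timing are assumed.

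It is also fair that these outcomes lie outside the fixed-sequence test, and that death is collected at every postoperative visit, so an imbalance would be visible.

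What the objection does not remove is the gap. The ICU definition does score an early death as a short stay, and no section corrects for it. That the sign of the result turns on when patients die is itself a reason to fix the rule beforehand, particularly in an open-label trial.

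**Conclusion.** The point holds as a minor one, on secondary outcomes only. For ICU stay, the plan as written turns an early death into a favourable value. For ventilation, the handling of a death while intubated is unspecified, and exclusion is the likely but unstated result.

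Under the stated assumptions at 5% vs 15% mortality, the effect on mean ICU stay runs from about 0.4 day in favour of the deadlier arm (all deaths on day 1) to 0.9 day against it (median death at 10 days). At Table 1 mortality the false shift is at most about 0.09 day. The primary composite counts death, so neither confirmatory hypothesis nor the sample size changes.

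One related ambiguity should be settled at the same time. The per-protocol set is described as "including all subjects who completed the trial without major protocol violations". If death before 12 months counts as not completing, the per-protocol analyses of these durations become survivor-only. The text does not say.

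**What to change.** In the two outcome definitions and in Secondary Endpoint Analysis, state that:

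- ICU stay and ventilation time are compared to day 30 by the rank-sum test already allowed under General Principles;
- patients who die within 30 days receive the worst rank, below survivors who are still in ICU or still ventilated at day 30;
- survivor-only times are reported descriptively, beside mortality by arm.

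Also state whether a patient who dies counts as having completed the trial for the per-protocol set.

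ICU-free or ventilator-free days with death scored 0 are a reasonable alternative but not the same analysis, because survivors still in ICU or ventilated at day 30 would tie with deaths. A competing-risk analysis would also serve. One method should be chosen and named before outcome data are seen.

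The cost is a few sentences and simple programming, with no new data, visits or patients. The downside is that the result is a rank effect mixing death with duration, rather than a difference in raw days, which is why the descriptive survivor times are needed alongside it.
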